1.0 Objectives

1.1 Study Objectives

- Compare pain, using a visual analog scale (VAS), associated with corticosteroid/lidocaine injection (CSL) to corticosteroid injection alone (CS) and corticosteroid/saline (CSS) injection.
- Review any adverse events related to the three treatment groups (CSL, CS and CSS).
- Review the efficacy of the three treatment groups (CSL, CS and CSS).
- Subcategorize patients based on demographic variables, comorbid conditions and anatomic location.

1.2 Primary Study Endpoints

- Compare pain and efficacy associated with the three treatment groups.
 - VAS and mean daily pain values

1.3 Secondary Study Endpoints

- Incidence of adverse effects
- Presence of clicking/locking (yes/no)
- Patient satisfaction (yes/no)
- Time to stopping medication
- Need for additional analgesics
- Effectiveness of injection

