7.2.3 Study Visit Flowsheet

Screening Visit – Visit 1	6-Week Follow-Up – Phone Call
Enrollment, Randomization, Pre-injection VAS, Injection, Post-injection VAS x 2, objective hand exam (SOC)	VAS, trigger question

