9.2 Statistical methods

The daily average pain score (VAS) will be compared between groups using either t-test or Wilcoxon test for each of the 6 days after the operation. Chi-square tests will be used to compare treatment groups for categorical variables (satisfaction, presence of clicking/locking, adverse events). Level of significance will be set at $p < 0.05$.

Secondary statistical analysis will include multivariate analyses to determine which variables such as anatomic location and comorbidities will impact the VAS score or modify the efficacy of injection. These can be accomplished by adding these variables and their interaction with treatment groups in the regression model. As these are secondary analysis, any interesting findings will be subject to validation in future studies.

Any deviations from the previously described statistical plan will be described and justified in a protocol amendment.

All analyses comparing the treatment groups will be conducted on an intention-to-treat basis. Two-tailed tests will be used at all times.

There will be an interim analysis when 50 % of patients (n=111) are enrolled and have completed final visit testing.

10.0 Confidentiality, Privacy and Data Management**10.1 Confidentiality****10.1.1 Identifiers associated with data and/or specimens**

See the Research Data Plan Review Form

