11.2 Data that are reviewed

Data to be reviewed includes the VAS scale as well as incidence of adverse effects, and patient satisfaction.

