11.3 Method of collection of safety information

Data will be collected beginning after informed consent at time of enrollment through six weeks postoperatively. Data will be collected at the initial clinic visit and again via telephone six weeks post-injection. Adverse events will be collected as they occur.

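### Three of the six secondary endpoints (satisfaction, additional analgesics, time to stopping medication) have no described collection step, and the listed content of the six-week call has no adverse-event question

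*Combined protocol and SAP*

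**What the plan says.** Section 1.3 names six secondary endpoints: adverse effects, clicking or locking, satisfaction, time to stopping medication, additional analgesics and effectiveness of the injection. Two of them read, in full, "Time to stopping medication" and "Need for additional analgesics".

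Section 7.3 allows two contacts, one clinic visit and one telephone call six weeks after injection. Section 7.2.1 describes the Patient Survey as a VAS pain scale and a trigger question, given before injection and again at 1 and 10 minutes. It adds a hand examination at the same visit. Section 7.2.2 repeats the survey by telephone, asks how often the digit triggers, and refers to a phone script. The flowsheet in 7.2.3 gives the content of the call as "VAS, trigger question".

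On analysis, 9.2 states: "Chi-square tests will be used to compare treatment groups for categorical variables (satisfaction, presence of clicking/locking, adverse events". Section 11.2 states: "Data to be reviewed includes the VAS scale as well as incidence of adverse effects, and patient satisfaction". On safety, 11.3 says that data are gathered at the visit and by telephone at six weeks, and adds: "Adverse events will be collected as they occur". Section 11.1 provides for an adverse-event log.

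**The concern.** Each endpoint should be traceable from its definition, through a question or form at a stated time, to an analysis. For three of the six secondary endpoints the middle step is missing from the protocol. For two of those three the last step is missing as well.

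A coordinator who works from 7.2.2 and 7.2.3 would finish the six-week call without asking about satisfaction or analgesics. Participants are not seen again, and answers not obtained then would be hard to recover reliably. The chi-square test of satisfaction in 9.2 would have nothing to work on.

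Adverse events raise a narrower issue. They are a study objective (1.1), a secondary endpoint ("Incidence of adverse effects") and a between-arm comparison (9.2). A comparison of incidence needs the same enquiry in every arm. If the call has no standard question, the counts depend on what participants choose to mention.

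**Working it through.** No figure in the plan bears on this point, and the sample size in 9.1 does not enter it. The check sets the endpoint list in 1.3 beside the content of the two contacts and the analyses in 9.2.

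| Endpoint (1.3) | Clinic visit (7.2.1, 7.2.3) | Six-week call (7.2.2, 7.2.3) | Analysis in 9.2 |
|---|---|---|---|
| Adverse effects | not listed | not listed (but see 11.3) | chi-square |
| Clicking/locking | hand exam, trigger question | trigger question | chi-square |
| Satisfaction | not listed | not listed | chi-square |
| Time to stopping medication | not listed | not listed | none named |
| Additional analgesics | not listed | not listed | none named |
| Effectiveness of injection | VAS, trigger question | VAS, trigger question | through VAS and the regression model |

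The last row rests on an assumption. Section 1.3 does not define effectiveness, and I take VAS and triggering as its sources.

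**Count.** Satisfaction, time to stopping medication and additional analgesics each appear at 0 of 2 contacts. That is 3 of 6 secondary endpoints, or 3/6 = 50%.

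**Other places where collection might be described.**
- Section 7.4.4 restates the schedule and again names only the Patient Survey.
- Section 7.4.6.4, where recording of concomitant medication would be expected, only points to the exclusion criteria.
- Section 11.2 names satisfaction among the data reviewed, but gives no instrument and no time point.
- No diary or medication log is described anywhere.

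**Time to stopping medication.** Sections 7.2.1 and 7.4.2 describe a single injection, and no continuing study medication is prescribed. Section 1.3 does not say which medication is meant. The endpoint needs a named medication, a stop date and a rule for participants who have not stopped, and none of these is given.

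**Adverse events.** Sections 11.1 and 11.3 provide a log, reporting during the study, and safety data by telephone at six weeks. Sections 7.2.2 and 7.2.3 list the content of that same call without an adverse-event question. The two descriptions of the call do not match. A route exists, but the question that would make enquiry uniform is not stated.

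**The case against.** The strongest reply is that neither the phone script nor the survey form is among the documents, and either could hold more items. Section 11.2 lists satisfaction as reviewed data, which suggests that someone meant to collect it. This stands as a limit on certainty. It does not remove the gap. Section 7.2.2 cites the script in connection with triggering, and both places that list the call's content omit the missing items. If the script already contains them, the protocol and flowsheet should say so.

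A second reply concerns safety, and it is largely right. A reader might infer that adverse events would have no data, or that no scheduled contact covers them. The documents do not support that, because 11.3 names the six-week telephone contact as a source of safety data and 11.1 provides a log. Only the mismatch with the listed content of the call remains.

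Third, a reader might infer that time to stopping medication is impossible to measure because there is one injection. It may refer to analgesics, since it stands directly above that endpoint in 1.3. The endpoint is undefined, not shown to be impossible, and whether to keep it is the sponsor's choice.

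Fourth, it is tempting to say that 9.2 and 11.2 promise analyses of all these endpoints. They name satisfaction and adverse events (9.2 also names clicking or locking, and 11.2 the VAS). Analgesic need and time to stopping medication appear only in 1.3.

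Finally, a reader might infer that unrecorded analgesic use distorts the six-week VAS comparison. The documents give no figure from which to size such an effect and no reason to expect it to differ between randomised arms, so it is not part of this point.

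**Conclusion.** The point holds in a limited form. Three of six secondary endpoints have no collection step described in the protocol. One of the three, satisfaction, has a planned test. The other two have neither collection nor analysis, and one of those does not name the medication it concerns. Separately, the listed content of the six-week call lacks the adverse-event question that 11.3 implies, so incidence may rest on spontaneous reports and be incomplete.

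That no collection is described can be checked directly in the text. That the data would in fact be missing is less certain, because it assumes the unseen script and survey form contain nothing beyond what 7.2.1 to 7.2.3 list. Followed as written, the three endpoints could not be reported. The VAS measurements before injection, at 1 and 10 minutes and at six weeks are unaffected, so the primary comparison does not depend on this. The change should be made, but the trial's main question does not turn on it.

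**What to change.** Amend 7.2.2, 7.2.3 and the phone script so that the six-week call includes:

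- a yes/no satisfaction item;
- a yes/no item on any additional analgesics since the injection;
- one standard adverse-event question, worded and asked the same way in all three arms.

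For time to stopping medication, either define which medication is meant and collect the stop date, or remove the endpoint from 1.3. If it stays, note that a date first asked for at six weeks relies on recall. Name in 9.2 the analysis for each of the two endpoints that currently have none, if they are kept.

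If the script already contains any of these items, the change reduces to listing them in 7.2.2 and 7.2.3. The cost is a slightly longer call that is already planned, and a small amendment. No extra contact is needed.

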2.0 Background

2.1 Scientific Background and Gaps

Trigger finger, or stenosing tenosynovitis, is a condition in which the flexor tendon is prohibited from gliding through the tendon sheath because of thickening of the synovial sheath over the tendon.¹ As a result, digital movement is impaired, and the affected digit locks in either flexion (the most common position) or extension, resulting in pain and swelling. Trigger digit pathology can be associated with

occupations involving lifting or gripping, but it also is associated with systemic disease states, such as rheumatoid arthritis and diabetes mellitus.² Trigger finger has a reported incidence of 28 cases per 100,000 subjects annually, or a risk of 2.6% over a lifetime.³ A survey of 516 patients treated between 1975 and 1994 indicated that 61% of trigger fingers occurred in women.⁴

Multiple approaches are available for both operative and non-operative management of trigger finger. Splinting, corticosteroids (either single or multiple injections), percutaneous surgery, and open surgery are all established means of treatment. A single injection of corticosteroid can provide symptom relief in 47% to 87% of patients with trigger finger.⁷⁻¹¹ According to Newport et al,¹³ each additional corticosteroid injection resulted in diminished efficacy. Corticosteroid injection has been widely accepted as first line treatment.^{8,9,14-16} When splinting and/or corticosteroid injections fail, surgery is recommended.¹⁴ Lidocaine is commonly used in conjunction with a corticosteroid because of its local anesthetic effect and near-immediate relief of pain. This dilution and increase in overall volume can aid in confirmation of medication delivery to the appropriate tissue and encourage diffusion of the steroid crystalline suspension to the entire area of interest. Though corticosteroids have a relatively quick onset of action, it may take 24 - 48 to notice symptom relief related to their prolonged anti-inflammatory effect, therefore lidocaine usually provides immediate, although, short-acting relief of pain. Lidocaine is extremely painful upon injection and may be an unnecessary addition to the steroid suspension. Addition of lidocaine also increases the volume of the injection, which may be a source of pain upon deposition into the flexor tendon sheath and subcutaneous tissues of the finger.

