2.2 Previous Data

Previous studies have evaluated the efficacy of steroid injections as compared to placebo injections in the treatment of trigger finger but no previous studies have compared steroid/lidocaine injections to injections without lidocaine. The aim of this study is to compare post-injection pain and efficacy of trigger finger injection using a combination of lidocaine/corticosteroid versus corticosteroid injection alone or corticosteroid/saline (equal volume). Our hypothesis is that lidocaine causes unnecessary pain upon injection and does not improve the efficacy of the steroid in providing sustained anti-inflammatory benefit. We also seek to determine if volume of injection plays a role in immediate post-injection pain (corticosteroid/saline group).

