7.2 Study Procedures**7.2.1 Visit 1 – Screening/Baseline Visit**

Patients will be given information about the study and asked to participate. If eligible, based on inclusion and exclusion criteria, informed consent will be obtained at the time of the screening visit and the patient will be enrolled in the study.

After obtaining informed consent, the patient will be randomized to one of three treatment groups. The study investigator (who is unblinded) will randomly draw a sealed envelope

containing one of the three treatment groups. The sealed envelopes will be stored in a secure area within the clinic practice site.

- CS – corticosteroid alone -1 cc dexamethasone (4mg/ml) only
- CSL – corticosteroid/lidocaine combination - 1 cc dexamethasone (4mg/ml) and 1 cc 1% lidocaine
- CSS – corticosteroid/saline combination - 1 cc dexamethasone (4mg/ml) and 1 cc 0.9% injectable saline)

The patient will then be asked to complete a Patient Survey pre-injection (VAS Pain Scale and Trigger question). The study investigator will perform a single injection using a 25 gauge 1.5" needle. The needle will be inserted at 90 degrees to the skin, 1 cm proximal to the metacarpophalangeal joint flexion crease. The injections will be prepared in the Bone & Joint Institute as part of standard of care.

The patient will then complete the Patient Survey at 1 minute and 10 minutes following injection (VAS Pain Scale and Trigger question).

Objective hand exam will be performed including range of motion at MP, PIP and DIP joints, presence of clicking or locking, triggering score, pain with range of motion and grip strength as part of the patient's standard of care.

7.2.2 6-Week Follow-Up Phone Call

The patient will be contacted via phone and will be asked to verbally complete the Patient Survey (patient will be asked to report the VAS Pain score over the phone in .5 increments – i.e. 3.5, 4.0, 5.0, 5.5, etc.) and the coordinator will record the score. The patient will also answer question about how often he/she triggers (see phone script).

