7.3 Duration of Participation

Subjects will only be seen in the clinic site once (time of enrollment in study) and will be contacted via telephone six weeks post-injection.

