7.4.4 Subject Compliance Monitoring

After obtaining informed consent, patients will be randomized to one of three recruitment groups. They will then be asked to complete a Patient Survey pre-injection and again 1 minute and 10 minutes after injection. They will be contacted via phone at six weeks post-injection and asked to verbally complete the Patient Survey.

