13.2 Potential Benefits to Others

The results of this study will guide future treatment decisions.

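### No pain reading is scheduled between 10 minutes and 6 weeks, so neither early relief from lidocaine after minute 10 nor the daily pain measure in 1.2 and 9.2 can be observed

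*Combined protocol and SAP*

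**What the plan says.** **Role of lidocaine.** Section 2.1 describes a delay before the steroid is felt and what lidocaine does meanwhile: "it may take 24 - 48 to notice symptom relief related to their prolonged anti-inflammatory effect, therefore lidocaine usually provides immediate, although, short-acting relief". No unit follows the 24 to 48; hours is the natural reading and is assumed here. No duration is given for lidocaine's effect.

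**Hypothesis.** Section 2.2 states: "Our hypothesis is that lidocaine causes unnecessary pain upon injection and does not improve the efficacy of the steroid". The sentence then restricts the efficacy part to the steroid's lasting anti-inflammatory effect.

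**Endpoints and analysis.** Section 1.2 lists the VAS and mean daily pain as primary measures. Section 9.2 compares the groups on the daily average VAS for 6 days. Section 1.3 adds use of extra analgesics and time until medication is stopped.

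**Schedule.** Section 7.2.1 takes a survey before injection, and then: "The patient will then complete the Patient Survey at 1 minute and 10 minutes following injection". Section 7.3 provides one clinic attendance, after which patients "will be contacted via telephone six weeks post-injection". Section 7.4.4 agrees: "They will be contacted via phone at six weeks post-injection and asked to verbally complete the Patient Survey". Sections 7.1, 7.2.2, 7.2.3 and 11.3 give the same contacts. None mentions a diary or a call in the first days.

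**The concern.** Early pain relief is the benefit specific to lidocaine in the protocol's own account. The other advantage in 2.1, a larger volume to help delivery and spread, can also come from saline, which is what the equal-volume CSS arm supplies. A trial that compares CSL with CSS would be expected to follow pain through the hours in which that relief appears and fades.

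The schedule follows it for 10 minutes and then stops for 6 weeks. Suppose CSL patients score worse at 1 minute and the same at 6 weeks. Lidocaine would look like added pain for no return. If CSL patients were also more comfortable for the rest of that day, or had rebound pain as the anesthetic wore off, the data would show neither.

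The plan itself treats the first days as important, since mean daily pain is a primary measure. The analysis asks for data that no procedure collects.

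**Working it through.** No figure in the plan is in dispute here, so the check sets the pain readings the plan needs beside those it collects.

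**1. Readings collected** (7.2.1, 7.2.2, 7.2.3, 7.4.4): before injection, 1 minute, 10 minutes, 6 weeks. The longest interval is 6 × 7 = 42 days less 10 minutes, or 42 − 10/1,440 = 41.99 days. It contains no scheduled reading.

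**2. Readings required by 9.2:** a daily average on each of 6 days. Section 9.2 counts these days from an operation, although the treatment is an injection, so the start needs an assumption.
- If day 1 is the day after injection, 0 of 6 days have a reading.
- If day 1 is the injection day, 1 of 6 days has post-injection readings. There are two, both within 10 minutes, which is not a daily average.

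**3. Other possible sources.** The two analgesic and medication endpoints in 1.3 have no stated tool or collection time. The flowsheet in 7.2.3 lists only the VAS and the trigger question at 6 weeks. Adverse events are taken as they occur (11.3), but that is not a pain score on every patient. The phone script named in 7.2.2 is not reproduced in the document. As described there, the call covers the survey and how often the finger triggers.

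**4. What each question can draw on**

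| Question | Reading available |
|---|---|
| Pain from the injection | 1 and 10 minutes |
| Start of lidocaine relief | 10 minutes |
| Relief, wearing-off or rebound later on day 0 | none |
| Pain on the following days | none |
| Sustained efficacy | 6 weeks |

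**5. Can the missed benefit be sized?** Let D be the duration of lidocaine relief in minutes. The share of that time after the last early reading is 1 − 10/D for D of 10 or more.
- D = 10: 1 − 10/10 = 0%.
- D = 120 (2 hours, an arbitrary illustration): 1 − 10/120 = 91.7%.
- D = 1,440 (24 hours, hard to square with short-acting): 1 − 10/1,440 = 99.3%.

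The documents do not give D, so the share could lie anywhere in this range. It also measures time, not amount of relief.

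**6. Effect on sample size.** Section 9.1 uses a 5 mm difference and an SD of 10 mm; 9.2 sets two-sided 0.05. Power is not stated. Assuming 80%, a t-test needs 63.8, so 64 per arm, and 3 × 64 × 1.15 = 220.8, so 221, as stated. Section 9.1 names no time point, and adding readings does not change this calculation.

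**The case against.** The strongest reply is that the trial tests what it set out to test. The hypothesis in 2.2 has two parts: pain on injection, and lasting steroid benefit. The readings at 1 and 10 minutes serve the first and the 6-week call serves the second. In that sentence, unnecessary describes the injection pain. The broader idea that lidocaine may not be needed at all is a background remark in 2.1, not an objective in 1.1 or an endpoint in 1.2. Section 2.1 also describes the relief as nearly immediate, so the 10-minute VAS can show a benefit, including CSL scoring below CSS. All of this stands. A reader might infer that the trial cannot judge lidocaine, or that it measures only harm; the documents do not support either.

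A second reply is that this is only a consequence of the conflict between 9.2 and the visit schedule, and that collecting daily pain would remove it. That is largely right, and the two should be resolved together. Two things remain. If 9.2 were instead rewritten for the readings now taken, early pain would stay unobserved. If daily scores were collected only from the day after injection, the later hours of day 0 would still be missing, and those suit a short-acting drug best.

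A third reply is that the statement in 13.2, "The results of this study will guide future treatment decisions", claims nothing about early relief. That is correct, and 2.2 makes no such claim either, so rewording those two sections would achieve little.

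**Conclusion.** The concern holds in a limited form. The trial can compare the arms on injection pain, the start of relief at 10 minutes, and status at 6 weeks. It cannot compare them on relief, wearing-off or rebound pain over the rest of the injection day and the days after, and the daily pain measure has no data source.

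The size is a gap of 41.99 days without a scheduled pain score, and at most 1 of the 6 planned days with any reading. This assumes that no unseen form collects early pain; no section mentions one.

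A reader might divide 10 minutes by the 24 to 48 hours (10/1,440 = 0.69%; 10/2,880 = 0.35%) and infer that over 99% of lidocaine's benefit goes unmeasured. The documents do not support that. The 24 to 48 is the time to steroid relief, and 2.1 never says that lidocaine lasts through it. The benefit missed may be small or large; the documents cannot settle which.

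**What to change.** Amend 7.2.1 and 7.2.3 to give each patient a take-home card with the same VAS anchors. It should have at least one reading later on the injection day and then one on each of the 6 days in 9.2, so at least 1 + 6 = 7 readings, read out at the existing 6-week call. The exact hour on day 0 is for the investigators to choose and state.

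Make the card the data source for the daily pain endpoint, so that no separate outcome competes with 1.2. Revise 9.2 to count days from the injection, to say whether a single daily score stands in for the daily average, and to name CSL against CSS (equal volume) as the comparison for the day-0 and early-day readings. Section 9.2 already requires changes to the statistical plan to go through an amendment.

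The cost is a printed card, one amendment and a slightly longer call, with no added visit, staff or patients. Some cards will be lost, incomplete or filled in late, so completion should be reported by arm.

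If no card is added, remove the daily pain endpoint from 1.2 and 9.2 and limit conclusions to pain at 1 and 10 minutes and status at 6 weeks. That costs only the wider claim.
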